Main study (WP2): The main study (WP2) will be a population based propensity score-matched cohort study using CPRD and HES collected datasets. The cohort of participants in this study will be young adults (aged 16–35 years) with traumatic anterior shoulder dislocation (T ASD) with at least 2 years data entry in CPRD before the their first shoulder dislocation code and at 2 years follow up from their first dislocation code entry in CPRD. All events and outcomes will be collected using a pre-agreed validated list of READ CODES (CPRD) and OPCS 4.7 CODES (HES). These codes are listed in the appendices and have already been identified. They will be further validated and informed by WP1. The first read code entry in CPRD for shoulder dislocation will be defined as the ‘first dislocation’. These codes will then be routinely linked to patients and to HES.

The ***Intervention group*** will be patients in CPRD with first time T ASD who underwent shoulder stabilisation surgery after their first dislocation (early surgical repair in this NHS context will mean ‘a decision to treat surgically after the first T ASD’ and receiving surgery within 6 months). This means linking HES data to CPRD data in such a way that a HES surgical OPCS 4.7 code is seen to occur after a single first dislocation code in CPRD (without further dislocation codes) before that surgical date. The timelines between first dislocation codes and OPCS 4.7 codes will be recorded. The ***Control group***. While the most desirable control group would be physiotherapy, it is possible that WP1 will reveal that free text notes and referral codes on physiotherapy will be lacking and not reliable. If this is the case then conservative care will be defined as ‘non surgical intervention’ with no linked OPCS 4.7 surgical shoulder codes producing a control cohort of patients whose first time shoulder dislocation has been treated non-operatively. If however free text entries and referral codes for physiotherapy are reliably present in CPRD then conservative care will be physiotherapy identified by physiotherapy referral codes after a first time T ASD code. Any subsequent dislocation codes or OPCS 4.7 surgery code will be recorded.

This project was funded by the National Institute for Health Research Health Technology Assessment (project number 14/160/01).

The views and opinions expressed therein are those of the authors and do not necessarily reflect those of the HTA, NIHR, NHS or the Department of Health.

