This commissioned call is directed at 'younger adults'. From age 40 years onwards instability and dislocation is associated with rotator cuff tears and the pathology and outcomes are different. Rotator cuff tears are highly rare below age 35 years and so our young target population will be patients aged 16-35 years in CPRD with a first time T ASD who underwent stabilisation surgery within 6 months of their first dislocation. We require a total sample size of 3065 with 656 expected total of re-dislocations. There are 26,534 patients in CPRD with recurrent anterior shoulder dislocations, and at least 10,449 of these patients will be aged 16-35 years with T ASD [7].

Inclusion criteria: Patients aged 16-35 years of age with a first time traumatic anterior dislocation (T ASD); patients that can be linked by CPRD and HES; minimum two year follow up period in CPRD.

Exclusion criteria: Surgery after more than one dislocation; instability treated with a rotator cuff repair or fracture surgery. We will also exclude:

- Patients aged 16-35 years with first time T ASD who cannot be linked by CPRD-HES
- Patients with less than two year follow up in CPRD
- Surgery after more than one T ASD
- Instability treated with rotator cuff repair surgery or fracture surgery.

J. Selection of comparison group(s) or controls

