The ***Intervention group*** will be patients in CPRD with first time T ASD who underwent shoulder stabilisation surgery after their first dislocation (early surgical repair in this NHS context will mean 'a decision to treat surgically after the first T ASD' and receiving surgery within 6 months). This means linking HES data to CPRD data in such a way that a HES surgical OPCS 4.7 code is seen to occur after a single first dislocation code in CPRD (without further dislocation codes) before that surgical date. The timelines between first dislocation codes and OPCS 4.7 codes will be recorded. The ***Control group***. While the most desirable control group would be physiotherapy, it is possible that WP1 will reveal that free text notes and referral codes on physiotherapy will be lacking and not reliable. If this is the case then conservative care will be defined as 'non surgical intervention' with no linked OPCS 4.7 surgical shoulder codes producing a control cohort of patients whose first time shoulder dislocation has been treated non-operatively. If however free text entries and referral codes for physiotherapy are reliably present in CPRD then conservative care will be physiotherapy identified by physiotherapy referral codes after a first time T ASD code. Any subsequent dislocation codes or OPCS 4.7 surgery code will be recorded.

K. Exposures, Outcomes and Covariates

As part of this application, we have performed a consensus survey of specialist shoulder surgeons and shoulder physiotherapists who are all members of the British Elbow and Shoulder Society. Saturation point and a list of predictors was reached rapidly and this list is tabulated in Appendix E and highlights the risk factors (and covariates) deemed most important. It is unlikely that all of these will be available from routinely collected national datasets but our study design will allow us to confirm through WP1 those factors that are reliably collected and that can be used for full analysis in WP2.

L. Data/ Statistical analysis

The association of surgical versus non-surgical intervention on subsequent re-dislocation within 2-years. The primary outcome of interest is the time from a first time traumatic anterior dislocation to subsequent re-dislocation within 2-years. The exposure of interest is whether or not a patient received shoulder surgery. In randomized controlled trials each person has

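### No criterion checks the linked hospital record for a shoulder stabilisation before the first dislocation code, so a repeat repair can be counted as early surgery after a first dislocation

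*Protocol*

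**What the plan says.** Section F (Main study, WP2) sets the index event from primary care records alone: "The first read code entry in CPRD for shoulder dislocation will be defined as the ‘first dislocation". The look-back is also in CPRD: "at least 2 years data entry in CPRD before the their first shoulder dislocation code".

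The surgical arm, defined in Section F and repeated in Section J, is found by linkage, under this condition: "HES surgical OPCS 4.7 code is seen to occur after a single first dislocation code in CPRD (without further dislocation codes"). The bar on further codes runs up to the date of the operation, and membership also depends on the patient "receiving surgery within 6 months".

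If physiotherapy coding proves unreliable, the fallback controls are patients "with no linked OPCS 4.7 surgical shoulder codes producing a control cohort of patients" treated non-operatively for their first dislocation. No time limit is attached to the absence of surgical codes.

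Section I gives "Exclusion criteria: Surgery after more than one dislocation; instability treated with a rotator cuff repair or fracture surgery", and adds patients who cannot be linked to HES and those with under two years of follow-up. Appendix E, the confounder list, does not contain previous stabilisation. Its nearest item is the number of dislocations before surgical repair.

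**The concern.** Whether the index event is a first dislocation, and whether the operation follows only one dislocation, are both decided by counting CPRD dislocation codes. The operation rule looks forward from the index code. Nothing looks backward in HES for an Appendix C operation, although every included patient must be HES-linked.

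Suppose a patient was stabilised before the CPRD look-back began, or after a dislocation the GP never coded. That patient later has one coded dislocation and is re-operated within six months. Every operational rule for the surgical arm is then met. Under a literal reading of the fallback definition, the same surgical history would bar the patient from the controls.

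The exposure would then mix primary and repeat repair, and any excess re-dislocation risk in the repeat cases would be charged to early surgery. Matching could not correct this under the fallback definition: previous stabilisation is not a listed covariate, and no control could carry it.

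**Working it through.** **1. Which rules could catch an earlier stabilisation?**

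| Rule | Where | Does it look for an operation before the index code? |
|---|---|---|
| First dislocation = first CPRD dislocation code | Section F | No; dislocation codes only |
| Two years of earlier CPRD data | Section F | No; requires CPRD history, not a clear HES record |
| Surgical code after a single dislocation code | Sections F, J | No; looks after the index code only |
| Surgery after more than one dislocation excluded | Section I | In intent; Sections F and J apply it by counting CPRD codes |
| Cuff repair or fracture surgery excluded | Section I | No; different operations |
| Propensity covariates | Appendix E | No; previous stabilisation not listed |
| GP questionnaire, question 5 | Appendix I | No; asks about earlier dislocation, in the validation sample only, and both answers lead to question 6 |
| No linked surgical shoulder code | Sections F, J, fallback controls | Yes, read literally, but in the controls only |

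Appendix D adds to the plausibility. Its index codes include a history-of-dislocation code (6,724 events) and three recurrent codes (2,140 + 1,321 + 599). Together these are 10,784 of the 81,672 listed events, about 13%. They are events, not patients or index events, so this is not an estimate of the number affected.

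**2. Reproducing the plan's figures (Section G).**
Inputs: 25% v 20% at two years, two-sided 5%, 90% power, 10% loss, equal groups.
- HR = ln(0.80)/ln(0.75) = 0.776; the protocol rounds this to 0.78.
- Events, Schoenfeld: 4(1.960 + 1.282)²/(ln 0.7757)² = 652. Freedman gives 659. The protocol's 656 lies between them.
- With 10% loss as a constant hazard, η = −ln 0.9, each arm's event probability is λ/(λ+η) × (1 − e^−(λ+η)), with λ = −ln 0.75 or −ln 0.80. The mean is 0.2140, and 656/0.2140 = 3065, as stated.

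The protocol's figures are not in dispute.

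**3. Illustration of size.**
Assumed, not in the document: a share p of the surgical arm are repeat repairs, with r times the planned 20% risk.
- Surgical risk = 0.20(1 − p) + 0.20·r·p
- HR = ln(1 − risk)/ln(0.75)
- Power = Φ(√(656/4) × |ln HR| − 1.96), where √(656/4) = 12.81

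| r | p | Surgical risk | HR | Power at 656 events |
|---|---|---|---|---|
| 1 | any | 20.0% | 0.776 | 90% |
| 1.5 | 2% | 20.2% | 0.784 | 87% |
| 1.5 | 5% | 20.5% | 0.797 | 83% |
| 1.5 | 10% | 21.0% | 0.819 | 72% |
| 2 | 2% | 20.4% | 0.793 | 84% |
| 2 | 5% | 21.0% | 0.819 | 72% |
| 2 | 10% | 22.0% | 0.864 | 47% |

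Worked row (r = 2, p = 5%): risk = 0.19 + 0.02 = 0.21; HR = 0.2357/0.2877 = 0.819; |ln HR| = 0.199; 12.81 × 0.199 − 1.96 = 0.59; Φ(0.59) = 72%.

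Holding events at 656 is a simplification. At N = 3065 the higher risk yields slightly more events: 685 in the last row, with power of 48%.

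**The case against.** **Section I already excludes these patients.** It requires a first-time dislocation and bars surgery after more than one, without tying either to CPRD codes. This stands as to intent. But Sections F and J then say what the surgical rule means in practice, and that rule does not see an operation recorded only in HES.

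**The route is narrow.** It needs an earlier episode with no earlier GP dislocation code, then two years of CPRD data, one new coded dislocation, and re-operation within six months, all by age 35. A history code entered within two years of the start of the record would fail the look-back. This stands, and the number may be small. A reader might infer that repeat operations do enter the arm; the text shows only that they can.

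**An earlier operation is not proof of an earlier anterior dislocation.** A reader might infer that it is. Appendix C includes SLAP repair, posterior labral repair and unspecified endoscopic codes, and notes that some of its codes are usually used for other joints. Side is not addressed, so the earlier operation may have been on the other shoulder. This stands.

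**The arms need not be uneven.** The fallback wording can be read as treatment of the index event, and this asymmetry does not arise under the preferred physiotherapy definition. This stands; the unevenness depends on a literal reading of the fallback.

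**Work Package 1 and the updated analysis plan will deal with it.** Work Package 1 is to confirm first-time status, and an updated plan precedes Work Package 2. But question 5 asks about dislocation rather than surgery and triggers no exclusion. No step commits the study to a HES look-back.

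**Conclusion.** The point holds in a limited form. Following the eligibility and exposure rules as written can admit repeat repairs that the protocol's own first-dislocation criteria mean to keep out, and the linked data could identify at least some of them. Sections F, I and J fix these definitions, so this is not a detail left to a statistical analysis plan.

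The size is unknown. The document gives no count of patients with an earlier stabilisation and no re-dislocation risk for them, so both the 2–10% share and the 1.5- to 2-fold risk are assumptions. The effect runs from none (no excess risk) to a serious loss of power at the top of the range. The 47% figure should not be read as an expected result. No sample-size figure in the protocol is wrong because of this point.

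**What to change.** Add one exclusion to Section I, applied alike to both arms: a shoulder stabilisation dated before the first dislocation code. Identify it by:
- Appendix C codes that are glenohumeral-specific or carry site code Z81.3 or Z81.4; and
- only the shoulder-specific stabilisation or labral Read codes in Appendix A. The site-free joint codes and the general shoulder-operation codes should not be used, because they would remove true first dislocators who had an operation on another joint or for another shoulder problem.

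Also:
- state how side is handled: same shoulder where side is recorded, with a sensitivity analysis where it is not;
- say that the controls' no-surgery rule refers to treatment of the index dislocation;
- report the number excluded in each arm.

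The cost is an eligibility line and a query on data already linked. The cohort will be slightly smaller, and a few true first dislocators will be lost because their earlier operation was on the other shoulder or for another reason.

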Population: 10,449 patients aged 16-35 years in CPRD with TASD and two years follow up.

WP1: Internal and external validation of shoulder dislocation coding and treatments within a routinely collected dataset (CPRD).

WP2: Propensity score-matched cohort study using linked CPRD and HES. All events and outcomes will be collected using a pre-agreed list of READ CODES (CPRD) and OPCS 4.7 CODES (HES).

Exclusions: Surgery after more than one dislocation; instability treated with a rotator cuff repair or fracture surgery.

Intervention: Surgical repair within 6 months of first time T ASD.

Control: non-surgical intervention.

Outcomes: Rate of re-dislocation, identified by codes in CPRD for 2 years after either treatment.

Sample size: 3065 with 656 expected total number of re-dislocations (90% power, 5% significance).

Statistical analysis: Propensity scores, Cox regression modelling and Rosenbaum bounds sensitivity analysis for *Surgical versus non-surgical intervention on re-dislocation*. Multiple imputation methods, survival models and fractional polynomials for *Predictors of recurrent dislocations*.

C. Objectives, Specific Aims and Rationale

Aim 1. To study the association between surgical treatment (compared to no surgery) and recurrence rates following a first episode of traumatic anterior shoulder dislocation (T ASD) amongst young adults. **Aim 2.** To identify clinical predictors of further recurrent dislocations in young adults with traumatic anterior shoulder dislocation stratified by surgery and no surgery.

Objectives: Following the HTA commissioning brief, we plan to use routinely collected observational datasets (Clinical Practice Research Datalink (CPRD) and Hospital Episodes Statistics (HES)) to answer the research questions above. The size of routinely collected data in UK primary care (CPRD) and secondary care (HES) offers rapid observational data to uncertainties about treatments in an affordable and generalisable manner. We have planned a propensity score-matched cohort study, with the intention to minimise confounding. Propensity score matching is considered one of the best methods available to approximate to any results obtained from randomised controlled trials. To ensure further value for money and to confirm the ability of these datasets to answer this very specific commissioned question, we plan a two stage approach through Work Packages 1 and 2.

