Work Package 1: Data Validation of shoulder dislocation coding and treatments within a routinely collected dataset (CPRD). **Work Package 2:** Population based cohort study using routinely collected datasets (CPRD and HES).

Having run feasibility counts in CPRD and there are 26,534 patients with shoulder dislocations in the database. We expect at least 10,449 to be T ASD in 'young' patients aged 16-35 years of age [7] indicating a very substantial dataset to answer this commissioned call.

D. Background

This project and study has been commissioned by the HTA and as such has already been deemed necessary. We can confirm that since the commissioned call there have been no published systematic reviews, or RCTs that answer the commissioning brief.

Shoulder joint dislocations are the most common joint dislocations seen in hospital A+E departments (8.2-17 cases per 100,000 population/year) with 95% of traumatic glenohumeral dislocations being anterior [15]. Traumatic anterior shoulder instability can carry significant morbidity. Some in the clinical community still quote high re-dislocation rates of 85% [16] and 92% [17] despite more recent larger population studies. A small but highly cited Swedish population study was conducted by Hovelius [18]. This prevalence study was in a random sample of 2092 people aged 18 to 70 years. 1.7% of patients reported a history of dislocation. There was a male to female ratio of 3:1 overall but this ratio varied with age being 9:1 in the 21 to 30 years age group. Hovelius also looked at recurrent dislocation trends

This project was funded by the National Institute for Health Research Health Technology Assessment (project number 14/160/01).

The views and opinions expressed therein are those of the authors and do not necessarily reflect those of the HTA, NIHR, NHS or the Department of Health.

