APPENDIX D

TABLE OF CPRD DISLOCATION READ CODES

Description	READ Code	Number of clinical events currently recorded in CPRD
Dislocation or subluxation of shoulder	S41.00	51,162
Dislocation of shoulder NOS	S41z.00	11,578
H/O: dislocated shoulder	14G5.00	6,724
Closed reduction of dislocation of shoulder	7K6G300	2,878
Closed traumatic dislocation of shoulder	S410.00	2,240
Recurrent dislocation of shoulder – anterior	N083A00	2,140
Anterior dislocation of shoulder	S410111	1,864
Recurrent joint dislocation, of shoulder region	N083100	1,321
Recurrent subluxation of shoulder – anterior	N083C00	599
Closed traumatic dislocation shoulder jnt. Anterior (sub-coracoid)	S410100	439
Closed traumatic dislocation shoulder joint, unspecified	S410000	439
Closed traumatic subluxation, shoulder	S412.00	288

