Appendix I

GP CPRD Validation Questionnaire for the UK.TASH-D Study

Dear Colleague,

Thank you for completing this questionnaire as a practice connected to the CPRD database. The UK.TASH-D study will use the CPRD to investigate the treatment of first time traumatic anterior shoulder dislocation. As you know, shoulder dislocations often recur and we are investigating whether surgery makes recurrence less likely after a first episode. We will be completely reliant in the main phase of this study on electronic codes to identify recurrences.

Before starting the main phase, we need to know whether we can reliably identify ‘New dislocation episodes’ or whether these tend to be recorded as a ‘Review’ of the same problem (without a further dislocation occurring). Conversely, we need to know if codes apparently indicating a ‘further’ dislocation episode are in fact a ‘Review’ of the problem. We also need to confirm that codes recorded in primary care as ‘dislocation’ actually reflect this diagnosis, rather than less specific conditions affecting the shoulder.

We are therefore looking at a national sample of records that indicate a shoulder dislocation, and by completing the following questionnaire on your patient, you will help tell us:

- 1) Was this actually a traumatic shoulder dislocation?
- 2) Did further episodes occur over the following two years, and if so, how many true recurrences were recorded as ‘New’ episodes?
- 3) Were there any examples of ‘New’ recurrences being recorded as a ‘Review’ of the original problem?

If the coding proves valid and reliable, then a CPRD dataset will be linked to a Hospital Episode Statistics (HES) dataset to compare surgical versus conservative treatment (including physiotherapy) on recurrent dislocation rates. Our aim is that this will result in national pathway guidelines for the management of this condition in primary care.

Thank you in anticipation of your help

The UK.TASH-D study team.

Number	Question	Response (please tick)	
		Yes	No
1.	Is shoulder dislocation, an unstable shoulder, or shoulder instability caused by INJURY documented in the patient’s notes?	(If YES go to Q5)	(If NO go to Q2)
2.	Is shoulder trauma or shoulder injury documented in the patient’s notes?	(If YES go to Q3)	(If NO go to Q3)

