3.	Do MRI or X-ray imaging reports confirm a diagnosis of traumatic dislocation by mentioning the presence of Hill Sachs, Bankart lesion, labral tear, labral detachment, dislocation, relocation, bony Bankart?	(If YES go to Q5)	(If NO go to Q4)

This project was funded by the National Institute for Health Research Health Technology Assessment (project number 14/160/01).

The views and opinions expressed therein are those of the authors and do not necessarily reflect those of the HTA, NIHR, NHS or the Department of Health.

4.	Do Hospital letters from specialists or physiotherapists confirm traumatic instability or traumatic shoulder dislocation?	(If YES go to Q5)	(If NO go to Q8)
5.	Is there any record of a dislocation prior to the CPRD first registration date at your practice?	(If YES go to Q6)	(If NO go to Q6)
6.	Are there any further dislocation codes in the record during the 2 years after the first dislocation code?	(If YES go to Q6b)	(If NO go to Q6c)
6b.	If YES is it clear (for each one) that this is a further dislocation episode rather than simply a review of the problem?	(If YES go to Q7)	(If NO go to Q7)
6c.	If NO, have there been any further dislocations recorded during the following 2 years that are not electronically coded?	(If YES go to Q7)	(If NO go to Q7)
7.	Are there any physiotherapy treatment codes for 2 years after the first dislocation code?	(If YES go to Q7b)	(If NO go to Q7c)
7b.	If YES is it clear that this physio code indicates the patient received physiotherapy for their shoulder?	(If YES go to Q8)	(If NO go to Q8)
7c.	If NO, is there any documentation that the patient has received physiotherapy for their shoulder without a code being entered?	(If YES go to Q8)	(If NO go to Q8)
8.	If your specific responses to this questionnaire indicate that this patient has not had a traumatic shoulder dislocation but your reading of the notes or your knowledge of the patient suggest they might have please tick the YES box, otherwise tick the NO box.	The end – thank you	The end – thank you

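### Surgical eligibility and re-dislocation are defined by counting codes, and no WP2 rule separates a repeat code for the index injury from a new dislocation

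*Protocol*

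**What the plan says.** **Eligibility.** Section F (main study, WP2), repeated in Section J, requires the HES surgical code to be "seen to occur after a single first dislocation code in CPRD (without further dislocation codes) before that surgical date". Section F fixes the start of follow-up in the same way: "The first read code entry in CPRD for shoulder dislocation will be defined as the" first dislocation. The exclusions in Sections B and I are worded in dislocations rather than codes: "Surgery after more than one dislocation; instability treated with a rotator cuff repair or fracture surgery".

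**Outcome.** Section B gives it as "Rate of re-dislocation, identified by codes in CPRD for 2 years after either treatment". The introduction to the GP questionnaire (Appendix I) says: "We will be completely reliant in the main phase of this study on electronic codes to identify recurrences".

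**Code list.** Appendix D includes "Closed reduction of dislocation of shoulder" (7K6G300; 2,878 events) and a history-of-dislocation code (14G5.00; 6,724 events). Either can be entered for the index injury.

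**Validation.** The Appendix I introduction recognises that a code which looks like a further dislocation may be a review. Question 6b asks: "is it clear (for each one) that this is a further dislocation episode rather than simply a review of the problem". Section F says the study stops if first-time or recurrent coding is poor, says WP1 will further validate the code lists, and promises an updated analysis plan before WP2. The only numerical criterion is a positive predictive value (PPV) of at least 75%, set in the review of first-time patients.

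**The concern.** The operative unit is the code, while the clinical question concerns the episode. Suppose one injury is coded as an anterior dislocation on the day, as a closed reduction when the hospital letter arrives, and as a dislocation again at a review in week 3. That is three Appendix D codes for one event. If the patient is operated on at month 4, the single-code condition fails and a true first-time surgical patient is lost. If the patient is not operated on, nothing in the WP2 text stops the later codes from counting as a re-dislocation.

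Two things are at stake:
- **Selection.** The surgical group is restricted to patients whose injury was coded once before surgery, which is partly a selection on recording habits.
- **Outcome misclassification.** If false events are equally common in both groups, they pull the hazard ratio towards 1 and cost power. If they are more common in non-operated patients, they favour surgery. The second pattern is possible because surgical patients must be free of further codes until surgery (up to 6 months), while controls pass no such filter.

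**Working it through.** **1. The plan's own figure (Section G).** The inputs are 25% versus 20% at 2 years, two-sided 5%, 90% power, 10% loss and equal groups.
- HR = ln(0.80)/ln(0.75) = 0.776 (stated 0.78).
- Events, Schoenfeld: 4(1.960 + 1.282)²/(ln 0.776)² gives 652. Freedman gives 659. The stated figure is 656.
- With 10% loss as exponential censoring, P(event) = λ/(λ+θ) × [1 − exp(−(λ+θ))], where λ = −ln(1 − risk) and θ = −ln 0.90. This gives 0.2379 (control) and 0.1902 (surgical), mean 0.2140. Then 3065 × 0.2140 = 656.
- Power = Φ(|ln HR| × √656 / 2 − 1.96) = 0.90.

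The sample size is sound on its own inputs.

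**2. Equal false coding.** Let f be the share of patients without a true re-dislocation who get a false event. It is not in the documents; 2% to 20% is an assumption. Observed risk = p + (1 − p)f. HR and power follow as in step 1, at N = 3065.

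| f | Control | Surgical | HR | Events | Power | N for 90% (Schoenfeld) |
|---|---|---|---|---|---|---|
| 0 | 25.0% | 20.0% | 0.776 | 656 | 90% | 3,046 |
| 2% | 26.5% | 21.6% | 0.790 | 701 | 88% | 3,321 |
| 5% | 28.75% | 24.0% | 0.810 | 769 | 83% | 3,757 |
| 10% | 32.5% | 28.0% | 0.836 | 883 | 76% | 4,538 |
| 20% | 40.0% | 36.0% | 0.874 | 1,110 | 61% | 6,361 |

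**3. Unequal false coding with no true effect.** True risk is 25% in both groups, and the false rate in the surgical group is assumed to be half that in controls. HR = ln(1 − [0.25 + 0.75f/2]) / ln(1 − [0.25 + 0.75f]).
- f = 5%: ln(0.73125)/ln(0.7125) = 0.92
- f = 10%: ln(0.7125)/ln(0.675) = 0.86
- f = 20%: ln(0.675)/ln(0.60) = 0.77

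Steps 2 and 3 ignore the time-varying exposure in Section L.

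**4. What the 75% threshold would allow.** Suppose it were applied to recurrence codes and every true re-dislocation were coded. A true control risk of 25% would then be observed as 0.25/0.75 = 33.3%, so f = (0.333 − 0.25)/0.75 = 11%. A pass at 75% is therefore compatible with roughly the 10% row above.

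**5. Codes per patient.** The Appendix D counts sum to 81,672. Section C says "there are 26,534 patients with shoulder dislocations in the database". The ratio is 81,672/26,534 = 3.08. Without the history and recurrent codes it is 70,888/26,534 = 2.67.

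**The case against.** The strongest reply is that the protocol saw this problem and staged the study around it. WP1 examines later codes, question 6b asks about each one, poor recurrent coding stops the study, and an updated analysis plan follows. An episode window could reasonably sit in that plan. This stands as evidence that the hazard is recognised. It does not cure the text. The single-code condition is an operative rule stated twice, and nothing says it will change. The 75% threshold has no separate part for recurrence codes. Question 6b is a yes/no tick without dates, so it cannot supply an interval.

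It can also be said that the strict rule is a defensible way to keep surgery for recurrence out of the intervention group, and that only the eligibility condition states outright that a further code disqualifies. Both are fair. The outcome half of the concern rests on Section B and Appendix I together with the absence of a separating rule, so a repeat code can count as an event; the text does not say that it must.

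Three stronger readings are tempting, and the documents do not support them:
- A reader might infer from about 3.1 codes per patient that repeat coding is the norm. The counts cover all ages and include true recurrences, and the two figures may have different bases. Sections G and I even describe the same 26,534 as patients with recurrent dislocation. The ratio is only indicative.
- A reader might place all false events in the non-surgical group, which at f = 10% turns 25% versus 20% into ln(0.80)/ln(0.675) = 0.57. That needs no false code at all after surgery. The code-free condition ends at surgery, and post-operative reviews can be miscoded too.
- A reader might assume that the same share f of surgical patients is lost before surgery. That equates a 2-year rate with a window of at most 6 months.

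**Conclusion.** The concern holds. Followed as written, the protocol drops true first-time surgical patients who have a repeat code before surgery. It also leaves repeat codes free to count as re-dislocations in non-operated patients and after surgery. WP1 tests for the problem, but no result of it is linked to the WP2 definitions.

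The size depends on a frequency the documents do not give. At 2% to 5% equal false coding the damage is modest (HR 0.79 to 0.81, power 88% to 83%). At 10% to 20% it is serious (HR 0.84 to 0.87, power 76% to 61%). With half the false rate in the surgical group and no true effect, an apparent HR of 0.92 to 0.77 arises for f from 5% to 20%. The factor of one half is also an assumption. The direction of bias is therefore not settled: equal false coding hides an effect, while more of it in controls creates one.

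**What to change.** - Replace the single-code condition in Sections F and J with a single first dislocation episode.
- Commit to a pre-specified minimum interval between codes, set from WP1 before WP2 outcomes are analysed. The documents give no basis for a particular number of days now.
- Extend question 6b to record, for each later code, its date and whether it was a new dislocation or a review.
- State that closed-reduction codes within the interval, and history-of-dislocation codes after the index, do not by themselves make a new episode.
- Apply the rule identically to surgical eligibility, the exclusion for more than one dislocation, and the primary outcome in both groups.
- Add a WP1 criterion for recurrence codes, separate from the 75% threshold.
- Vary the interval in sensitivity analyses.

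The cost is protocol wording, a few lines of data-management code and extra fields in question 6b. There is a small downside: a true early re-dislocation inside the interval is merged into the index episode. A sensitivity analysis with a shorter interval addresses this.
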